### 2.5.2 Data handling conventions for secondary efficacy variables

#### *JIA-ACR component – joint counts with active arthritis/limited range of motion (AJC/LJC)*

When calculating the AJC and LJC, the joints with missing assessment will be imputed as the mean of the joints with assessment, ie, the AJC/LJC after imputation are as follows:

$$\text{AJC} = \text{sum (joints with active arthritis='Y')} * (71/\text{number of joints with assessment})$$

$$\text{LJC} = \text{sum (joints with limited motion='Y')} * (67/\text{number of joints with assessment})$$

Please note: the imputation will only be performed if the number of joints with missing assessment is  $\leq 7$  for each active arthritis or limited motion joints. If the number of joints with missing assessment is  $> 7$ , then the corresponding joint counts will be set to missing.

### ***JADAS-27 component – joint counts (27) with active arthritis (AJC27)***

When calculating the AJC27, the joints with missing assessment will be imputed as the mean of the joints with assessment, ie, the AJC27 after imputation is as follows:

$$\text{AJC27} = \text{sum}(\text{joints with active arthritis='Y'}) * (27 / \text{number of joints with assessment})$$

Please note: the imputation will only be performed if the number of joints with missing assessment is  $\leq 3$  for 27 joints. If the number of joints with missing assessment is  $> 3$ , then AJC27 will be set to missing.

### ***JIA-ACR component - CHAQ-DI***

The CHAQ questionnaire consists of 30 questions referring to eight domains; dressing/grooming, arising, eating, walking, hygiene, reach, grip and activities. Each domain has at least two component questions and there are five possible responses (0 = without any difficulty, 1 = with some difficulty, 2 = with much difficulty, 3 = unable to do, and “not applicable”). If any of the questions contain multiple responses, the worst case in terms of a patient’s health status will be assumed, this being the most conservative approach. A domain score is determined from the highest score (ie, worst response) of the questions in that domain. However, if specific aids and devices are used or assistance from another person is required in performing functional tasks, then the score of the respective domain is adjusted. If the domain score is 0 or 1, then the domain score is increased to 2, and if the domain score is 2 or 3, then the domain score is not adjusted. To calculate the overall CHAQ-DI score the patient must have a domain score for at least six of the eight domains. The CHAQ-DI score is the sum of the domain scores divided by the number of domains that have a non-missing score. This overall score ranges from 0 (best) to 3 (worst). Note that items marked as not applicable are not considered in the score calculation.

### **2.5.3 Missing data**

For categorical variables, patients with missing data are not included in calculations of percentages unless otherwise specified. When relevant, the number of patients with missing data is presented.

### ***Handling of computation of treatment duration if investigational drug end of treatment date is missing***

For the calculation of the treatment duration, the date of the last dose of IMP is equal to the date of last administration reported on the dosing CRF page. If this date is missing, the exposure duration will be kept as missing.

### ***Handling of medication missing/partial dates***

No imputation of medication start/end dates or times will be performed. If a medication date or time is missing or partially missing such that it cannot be determined whether it was taken prior or concomitantly, it will be considered as a prior and concomitant medication.

### ***Handling of AEs with missing or partial date/time of onset***

Missing or partial AE onset dates and times will be imputed so that if the partial AE onset date/time information does not indicate that the AE started prior to treatment or after the TEAE period, the AE will be classified as treatment-emergent. No imputation of AE end dates/times will be performed. These data imputations are for categorization purposes of treatment emergence only and will not be used in listings. No imputation is planned for date/time of AE resolution.

### ***Handling of AE when date and time of first IMP date is missing***

When the date and time of the first IMP is missing, all AEs that occurred after or on the day of inclusion will be considered as TEAEs. The exposure duration will be kept as missing.

### ***Handling of missing relationship to IMP of AEs***

If the assessment of the relationship to IMP is missing, then the relationship to IMP has to be assumed and the AE considered as such in the frequency tables of possibly related AEs, but no imputation will be done at the data level.

### ***Handling of missing severity of AEs***

If the severity is missing for one of the treatment-emergent occurrences of an AE, the maximal severity on the remaining occurrences will be considered. If the severity is missing for all the occurrences, a “missing” category will be added in the summary table.

### ***Handling of PCSA***

If a subject has a missing baseline, he/she will be grouped in the category “normal/missing at baseline”.

For PCSA with two conditions, one based on a change from baseline value or a normal range and the other one on a threshold value, the first condition being missing, the PCSA will be based only on the second condition.

For PCSA defined on a threshold and/or a normal range, the PCSA will be derived using this threshold if the normal range is missing; eg, for eosinophils the PCSA is  $>0.5$  Giga/L or  $>ULN$  if  $ULN \geq 0.5$  Giga/L. When ULN is missing, the value 0.5 Giga/L will be used.

Measurements flagged as invalid by the laboratory will not be summarized nor be taken into account in the computation of PCSA values.

#### **2.5.4 Windows for time points**

For efficacy parameters, discontinuation visit will be mapped to the scheduled visit for the analyses. If a discontinuation visit happens at a regular visit, then the visit number will be reassigned as the regular visit number where an assessment is planned. If a discontinuation visit happens between 2 regular visits, then the visit number will be reassigned to the next visit number where an assessment is planned. For example, if a discontinuation visit happens between Visits 5 and 6, then the visit number will be reassigned as 6.

Visit windows based on days relative to the first IMP dose will be used to map the laboratory values, vital signs, ADA, and PK measurements to each scheduled visit (see [Appendix B](#) for details). The following rule will be applied when mapping the measurements to the visit:

1. When a patient has more than one measurement on the same lab parameter (or vital sign) on the same date, then the one with the later/largest sample ID will be used.
2. For the same laboratory parameter (vital sign), if a patient has more than one measurement at different dates within the same visit window, the scheduled measurement that is closest to the target date will be used. If there is no scheduled measurement within the visit window, the unscheduled measurement that is closest to the target date will be used.
3. When a patient has more than one measurement on the same lab parameter with the same distance from the target date, the one with the latest date will be used.

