- j. Investigational medicinal product to be administered once every other week for patients in Dose Regimen 1 and 2 Cohorts and once every week for patients in Dose Regimen 3 Cohort. Arrangements will be made for home nurses to administer IMP for Dose Regimen 3 Cohort patients for the intermediate visits (home administration if possible). Patients should be monitored for at least 30 minutes after IMP administration for any signs or symptoms of a hypersensitivity reaction. For Germany only: After the first IMP administration the patient has to be monitored for at least 1 hour to assess local tolerability. In the dose-finding and second portions, patients who do not achieve a JIA American College of Rheumatology (ACR) 30 by the end of the 12-week core treatment period will be discontinued from the study treatment to receive standard of care as per the Investigator's clinical judgment. Juvenile idiopathic arthritis ACR response, including JIA ACR30 response, will be provided by the Sponsor to Investigator to evaluate this criterion only after Visit 12. For patients completing the core treatment phase at Visit 12 (Week 12), but not continuing to the extension phase for reasons other than lack of JIA ACR30 response, there will be no IMP injection at Visit 12.
- k. Investigational medicinal product will be dispensed to patients who are at the Dose Regimen 3 Cohort during the core treatment phase.

- l. Height will be measured using stadiometer at sites during the study.
- m. Juvenile Idiopathic Arthritis ACR core set includes: global assessment of the severity of disease by the physician, global assessment of overall well-being by the patient or the parent(s)/guardian(s), number of joints with active arthritis (defined as swelling not due to deformity OR limitation of motion with either pain or tenderness or both), number of joints with limitation of motion, Childhood Health Assessment Questionnaire (CHAQ), hs-CRP (2,3,4). At the Screening, only number of joints with active arthritis and number of joints with limitation of motion will be assessed.
- n. Juvenile Arthritis Disease Activity Score scoring is explained in [Section 9.4.2](#).

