1.2.2 Extension phase

In the dose-finding and second portions, only patients achieving at least a JIA ACR30 response at Week 12 will be permitted to continue to participate in the extension phase.

During the extension phase:

- Patients who were enrolled to the selected dose regimen during the core treatment phase (either during the initial dose-finding portion or directly to the selected dose regimen in the second portion) will continue on the selected dose regimen during the extension phase and will be followed-up as noted in [Section 1.2.2.1](#))
- Once the selected dose regimen has been determined, patients who were not assigned to the selected dose regimen will have their dose regimen adjusted to the selected dose regimen during the extension phase. Prior to dose adjustment, these patients will complete the assessments as noted in [Section 1.2.2.1](#). After the dose regimen is determined, the patients will have their dose regimen adjusted to the selected dose regimen at the time of their next regular scheduled visit (according to [Section 1.2.2.1](#)), which will be considered as the first visit (Visit 101 [Week 0]) as shown in the flow chart in [Section 1.2.2.2](#). These patients will then continue with the assessments as noted in [Section 1.2.2.2](#). All patients will remain on treatment until they have received up to a total of 144 weeks of sarilumab exposure calculated from Visit 12. A table to determine when the last on-treatment visit should occur and the weeks between the last on-treatment visit, and the EOT visit based on when the patient was changed to the selected dose regimen is provided in [Table 1](#). After the last on-treatment visit, patients will be scheduled for the EOT visit (Visit 27) and the EOS visit (Visit 28).
- Patients who are enrolled in the third portion with the selected dose regimen will be followed-up as noted in [Section 1.2.2.3](#).

1.2.2.1 Flow chart for patients who remain on the current dose (selected dose regimen) from the dose-finding portion or recruited directly under the selected dose regimen in the second portion

Visit	Extension phase (up to 144 weeks of sarilumab exposure from V12)														Post-treatment follow-up (6 weeks)		
	V13	V14	V15	V16	V17	V18	V19	V20	V21	V22	V23	V24	V25	V26		V27 ^a	V28 ^b

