Day	D 113 (±1 or 3)	D 141 (±1 or 3)	D 169 (±1 or 3)	D 225 (±1 or 3)	D 281 (±1 or 3)	D 337 (±1 or 3)	D 421 (±1 or 3)	D 505 (±1 or 3)	D 589 (±1 or 3)	D 673 (±1 or 3)	D757 (±1 or 3)	D 841 (±1 or 3)	D 925 (±1 or 3)	D 1009 (±1 or 3)	Wk 156/EOT	EOS: WK162/EOT+6 Wks
Week	Wk 16	Wk 20	Wk 24	Wk 32	Wk 40	Wk 48	Wk 60	Wk 72	Wk 84	Wk 96	Wk 108	Wk 120	Wk 132	Wk 144		
ANA/anti-dsDNA antibody ^l			X			X		X		X					X ^l	
Local urine pregnancy test for females who are menstruating ^m	X	X	X	X	X	X	X	X	X	X	X	X	X	X	X	
Pharmacokinetics and ADA																
Serum sarilumab ⁿ			X			X		X		X		X			X	X
Antibodies to sarilumab ⁿ			X			X		X		X		X			X	X

Abbreviations: ADA = anti-drug antibody, AE = adverse event, ALP = alkaline phosphatase, ALT = alanine aminotransferase, ANA = antinuclear antibodies, ANC = absolute neutrophil counts, AST = aspartate aminotransferase, BP = blood pressure, DNA = deoxyribonucleic acid, D = day, EOT = End-of-Treatment, EOS = End-of-Study, ESR = erythrocyte sedimentation rate, hs-CRP = high sensitivity C-reactive protein, IMP = investigational medicinal product, IVRS = Interactive Voice Response System, JADAS = Juvenile Arthritis Disease Activity Score, JIA ACR = Juvenile Idiopathic Arthritis American College of Rheumatology, PK = pharmacokinetics, PPD = Purified Protein Derivative, SAE = serious adverse event, TB = Tuberculosis, V = visit, Wk/Wks = week, yrs = years.

- Visit 27 (Week 156) is the study planned End-of-Treatment (EOT) visit. If patients discontinue the study treatment prematurely, EOT will occur 1 week after the last IMP injection for Dose Regimen 3 Cohort and 2 weeks after the last IMP injection for Dose Regimen 1 and 2 Cohorts.
- Visit 28 (Week 162) is the study planned End-of-Study (EOS) visit. If patients discontinue study treatment prematurely, these patients will be asked to return for the End-of-Study (EOS) assessment 6 weeks after the EOT visit (EOT+6 weeks). This EOS visit will be applicable to all the patients in both core treatment phase and extension phase.
- Home diary for IMP administration to be completed for IMP administered at home.
- Complete physical examinations will be performed at Visit 15 (week 24), Visit 18 (Week 48), Visit 20 (Week 72), Visit 22 (Week 96), Visit 24 (Week 120), Week 26 (Week 144), and Visit 27 (Week 156) including skin, nasal cavities, eyes, ears, respiratory, cardiovascular, gastrointestinal, neurological, lymphatic, and musculoskeletal systems.

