9.4 EFFICACY ENDPOINTS

9.4.1 Juvenile idiopathic arthritis American college of rheumatology response

The JIA ACR rating scale to assess signs and symptoms will be used in this study (refer to [Section 1.2](#)).

The JIA ACR 30/50/70/90/100 response is defined as a patient with 3 of 6 core set variables improved by at least 30%/50%/70%/90%/100% from baseline with no more than 1 of the remaining variables worsened by more than 30% [Appendix C](#). The JIA ACR core set includes 6 variables:

- Physician global assessment of disease activity
- Patient/parent assessment of overall well-being
- Functional ability determined by Childhood Health Assessment Questionnaire (CHAQ)
- Number of joints with active arthritis (0-71 joints)
- Number of joints with limitation of motion (0-67 joints)
- High sensitivity C-reactive protein.

During the 12-week core treatment phase, JIA ACR disease core set will be evaluated at every site visit except Visit 3 (Day 3), Visit 4 (Day 5), Visit 5 (Day 8), and Visit 6 (Day 12). During the extension phase (for patients who remain on the current dose (selected dose regimen), the JIA ACR core set will be assessed periodically at Weeks 24, 48, 72, 96 (EOT for third portion), 120 (not applicable for third portion), 144 (not applicable for third portion), and EOT (Week 156 for dose-finding and second portions/Week 96 for third portion). For patients who change to the selected dose regimen during the extension phase, please refer to [Section 1.2.2.2](#).

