10.1.10 Visit 27: End-of-Treatment visit

Visit 27 (EOS) will be Week 156 for patients enrolled in the dose-finding and second portions and Week 96 for patients enrolled in the third portion.

- Record all concomitant medications used with start date and dose in the patient's e-CRF
- Inquire regarding AEs/SAEs
- Record vital signs including body temperature, BP and HR
- Record patient weight (kg) and height (cm)
- Check Tanner stage and menstruation status for female patients (see [Appendix F](#))
- Check home diary/compliance
- Perform a complete physical examination including skin, nasal cavities, eyes, ears respiratory, cardiovascular, gastrointestinal, lymphatic, neurological systems, and musculoskeletal systems
- Perform the joint count assessments to note JIA disease manifestations (articular and extra-articular) and assess disease activity (ensure JADAS -27 joints are included)
- Ask the patient/parent(s)/guardian(s) to complete relevant questionnaires: functional ability determined by CHAQ and (parent or guardian)/patient assessment of overall well-being. All questionnaires should be documented in the subject's study file. Each VAS score should be copied on the patient's e-CRF
- Complete the physician global assessment of disease activity
- Perform a tuberculosis risk assessment. In case of suspicion of tuberculosis, refer the patient to a specialist for a complete examination and additional work-up

- Collect blood for hematology (see [Section 9.3.4](#)) and complete chemistry (including sodium, potassium, chloride, bicarbonate, BUN, glomerular filtration rate, creatinine, creatinine clearance, calcium, phosphate, total protein, albumin, ALT, AST, ALP, total bilirubin, conjugated bilirubin, and unconjugated bilirubin; see [Section 9.3.4](#))
- The IL-6 and total sIL-6R will be measured for patients who discontinue the study treatment prematurely during the core treatment phase
- Collect blood for hs-CRP, ESR, serum sarilumab, and antibodies to sarilumab
- Collect blood for fasting lipids and ANA/anti-dsDNA only for patients who discontinue prematurely before Week 96 (for the dose-finding and second portion)/Week 48 (for the third portion)
- Perform urine pregnancy test for female patients who have commenced menstruating
- Call IVRS to notify the patient's status (EOT)
- There is no IMP administration at this visit
- Check local tolerability (for patients who change to the selected dose; see [Section 9.3.3](#))

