#### Extension part:

- JIA ACR 30/50/70/90/100 proportion responders at weeks 24, 48, and every 24 weeks up to the end of the study
- JADAS-27 change from baseline at weeks 24, 48, and every 24 weeks up to the end of the study
- [REDACTED]
- █ [REDACTED]
- █ [REDACTED]

The JADAS includes 4 measures:

- Physician global assessment of disease activity (as previously defined)
- Parent or patient assessment of overall well-being (as previously defined)

- Count of joints (27) with active disease
- Index of inflammation: hs-CRP or ESR level
  - ESR normalized to a 0-10 scale according to the following formula:  
(ESR[mm/hour]-20)/10 where before making the calculation, ESR value <20 mm/hour converted to 0 and ESR value >120 mm/hour converted to 120.
  - Or hs-CRP normalized to a 0-10 scale according to the following formula:  
(CRP [mg/L] – 10)/10 where before calculation, CRP values <10 mg/L were converted to 0 and CRP values >110 mg/L were converted to 110.

The JADAS-27 will be calculated as the simple linear sum of the scores of its 4 components.

[REDACTED]

[REDACTED]

- [REDACTED]
- [REDACTED]

[REDACTED]

- [REDACTED]
- [REDACTED]
- [REDACTED]

[REDACTED]

[REDACTED]

[REDACTED]

- [REDACTED]
- [REDACTED]

[REDACTED]

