### 2.4.6.1 Analysis of JIA ACR30 response

Patients achieving JIA ACR30 [REDACTED] response for each dose regimen cohort, overall and by weight group, will be summarized by visit using counts, proportions and 95% CIs. The primary approach will be based on all observed data while the patient remains on treatment. No missing data will be imputed.

Additionally, for the summaries on the JIA ACR30 responses during the 12-week core treatment part, several different approaches will be used for the handling of treatment discontinuations and missing data.

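### Read literally, SAP 2.5.4 places the Week 13-14 end-of-treatment scores of portion 1-2 Week 12 ACR30 non-responders in the Week 24 extension efficacy summaries

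*SAP*

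**What the plan says.** **Entry to the extension.** Protocol 1.2.2 sets a response requirement for portions 1 and 2: "only patients achieving at least a JIA ACR30 response at Week 12 will be permitted to continue to participate in the extension phase". Portion 3 has no such requirement.

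**Dosing at Visit 12.** Under footnote j of the core-phase flow chart (Protocol 1.2.1), the ACR30 result "will be provided by the Sponsor to Investigator to evaluate this criterion only after Visit 12". The same footnote withholds the Visit 12 injection only from children who leave for some reason other than lack of ACR30 response.

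**Timing and content of EOT.** After premature discontinuation, "EOT will occur 1 week after the last IMP injection for Dose Regimen 3 Cohort and 2 weeks after the last IMP injection" for Regimens 1 and 2 (Protocol 1.2.2.1, notes). Visit 27 includes joint counts, both global assessments and the CHAQ. Its laboratory work includes this item: "Collect blood for hs-CRP, ESR, serum sarilumab, and antibodies to sarilumab" (Protocol 10.1.10). Full ACR and JADAS-27 scores are therefore available.

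**Next planned efficacy assessment.** In the extension, "the JIA ACR core set will be assessed periodically at Weeks 24, 48, 72, 96" and later (Protocol 9.4.1). The flow chart shows none at Visit 13 (Week 16) or Visit 14 (Week 20).

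**Mapping and analysis.** For a discontinuation visit between two regular visits, SAP 2.5.4 says of efficacy parameters: "then the visit number will be reassigned to the next visit number where an assessment is planned". It sets no time limit and makes no exception. The listed extension endpoints include "JIA ACR 30/50/70/90/100 proportion responders at weeks 24, 48, and every 24 weeks up to the end of the study" (SAP 2.1.5.2), with JADAS-27 change on the same schedule. For ACR30, "The primary approach will be based on all observed data while the patient remains on treatment" (SAP 2.4.6.1), without imputation.

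**The concern.** A Week 24 response rate should describe either the children who entered the extension or all children treated. As mapped, it describes neither. Week 12 non-responders were refused entry, yet they would appear at Week 24 with scores taken at Week 13 or 14. Children who stopped well before Week 12 would be absent, because their EOT maps to a core-phase visit.

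This is not occasional dropout. The protocol's own entry rule produces these children, and each one dosed at Visit 12 follows the same path. The non-responder, LOCF and post-discontinuation analyses in SAP 2.4.6.1 cover only the 12-week core part, so none of them corrects Week 24.

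**Working it through.** The plan states no figure to reproduce. The check is a visit calendar, followed by an illustration under assumed rates.

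**Calendar** (Protocol 1.2.1 and 1.2.2.1). Visit 12 is Day 85, Visit 13 is Day 113 and Visit 15 is Day 169.

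- Regimens 1 and 2: EOT = 85 + 14 = Day 99 (Week 14). Gap to Visit 15 = 169 - 99 = 70 days, or 10 weeks.
- Regimen 3: EOT = 85 + 7 = Day 92 (Week 13). Gap to Visit 15 = 169 - 92 = 77 days, or 11 weeks.
- Both days lie between Visits 12 and 13. The next visit with the core set planned is Visit 15.

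**Comparison within the SAP.** Appendix B, Table 1 places PK and ADA samples from Days 71 to 126 at Week 12. Drug level from this EOT would be labelled Week 12, while response from the same visit would be labelled Week 24.

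**Treatment epoch** (SAP 2.1.4: last dose + 13 days for dosing every other week, + 6 days for weekly dosing).

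- Every other week: 85 + 13 = Day 98; nominal EOT is Day 99.
- Weekly: 85 + 6 = Day 91; nominal EOT is Day 92.
- Visit windows are ±3 days and ±1 day (Protocol 6.3.1). EOT may therefore fall on Days 96-102, of which 96-98 are inside the epoch, or on Days 91-93, of which only 91 is inside.
- Portion 3 completers: last dose at Week 94 is Day 659; 659 + 13 = Day 672; the Week 96 EOT is Day 673, also one day outside.

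**Size.** Let n be the group size, k the number of Week 12 non-responders, p the Week 24 response among entrants, and e the number of the k who respond at EOT. If no entrant drops out before Week 24, the mapped rate is [p(n - k) + e]/n. It falls below the entrants' rate by (pk - e)/n.

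Assumption: p is about 90%. The documents show no ACR30 rate. For a group of 18 (Protocol 6.1: 18 evaluable per weight group at the selected regimen), in whole children:

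| Case | Entrants only | As mapped | Difference |
|---|---|---|---|
| k = 1, e = 0 | 15/17 = 88.2% | 15/18 = 83.3% | 4.9 points |
| k = 2, e = 0 | 14/16 = 87.5% | 14/18 = 77.8% | 9.7 points |
| k = 2, e = 1 | 14/16 = 87.5% | 15/18 = 83.3% | 4.2 points |

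With one stop well before Week 12 and k = 2, e = 0: entrants 13/15 = 86.7%, as mapped 13/17 = 76.5%, all treated 13/18 = 72.2%.

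If portion 3 is pooled, it adds 8 to 20 children per weight group (Protocol 8.4), so n = 26 to 38. Each non-responder then costs 0.9/26 = 3.5 points down to 0.9/38 = 2.4 points. Two cost 6.9 down to 4.7 points.

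**The case against.** **The mapping to Week 24 is not the only reading.** The SAP's own example sends a discontinuation visit between Visits 5 and 6 to Visit 6, where no efficacy assessment is planned. By analogy, this EOT would go to Visit 13 (Week 16), which is not a listed endpoint. That stands as an ambiguity. The rule is written for efficacy parameters, however, and refers to a planned assessment. Mapping to Visit 13 would also create a Week 16 ACR time point made up only of discontinued children.

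**On treatment has a possible definition.** A reader might infer that the phrase is undefined. It is not wholly so: the SAP 2.1.4 epoch would exclude an EOT on its nominal day, and the Week 24 effect would then be nil. But that definition sits in the safety section. Applied here, it would admit some EOT scores and drop others on a day or two of visit window, and it would lose the portion 3 Week 96 assessment, a listed endpoint. Week 156 would be lost too, but it is not on the 24-week endpoint schedule and carries no weight here.

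**The Week 12 dose is inferred.** Protocol 10.1.7 says to inject children who are going to enter the extension. A non-responder left undosed would have EOT at Week 12, and the problem would vanish for that child. Because the result is not known at the visit, footnote j is the workable rule.

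**The fix is narrow.** Forward mapping also applies to entrants who stop later; an EOT at Week 50 would be labelled Week 72. That is true, but those children did belong to the extension.

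**Conclusion.** The point holds as a literal consequence of SAP 2.5.4 that needs a clarifying rule. It is not proof that the analysis will be done this way. Week 13-14 scores would be labelled Week 24, and the Week 24 denominator would mix excluded children with entrants.

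A reader might infer that the rule inflates Week 24 response. The documents do not support that: most of these children would probably still be non-responders, so the likely effect is to lower the rate, towards the all-treated figure.

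A reader might also carry the group-of-18 figures over to every Week 24 table. They fit only summaries confined to portions 1 and 2, such as the second interim analysis. Pooling portion 3 reduces the shift to about 2.4-3.5 points per child. All sizes rest on an assumed 90% response among entrants, no dropout among entrants before Week 24 and, unless stated, no response at EOT.

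The effect is confined to secondary, descriptive efficacy. The primary PK endpoint is untouched, no test is planned, and portion 3 has no Week 12 response requirement to create the problem.

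**What to change.** In SAP 2.5.4:

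1. Exempt portion 1-2 children who stop for lack of a Week 12 ACR30 response from forward reassignment, and report their scores as EOT.
2. State that EOT scores from all other patients count as on treatment, so that the portion 3 Week 96 assessment is kept and inclusion does not depend on the visit window.
3. Report portion 1-2 Week 24 response among extension entrants and, beside it, over all treated portion 1-2 patients, counting Week 12 non-responders and earlier stops as non-responders.

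Two clarifications are optional. Protocol 10.1.7 could match footnote j by saying that every portion 1-2 patient is injected at Visit 12 except those leaving for other reasons. SAP 2.1.4 could say that a Week 12 non-responder's Visit 12 dose does not count as entering the extension.

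The cost is one rule with a flag for the reason for stopping, and one further denominator in the Week 24 tables. No new data are needed.
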